5.7.2 Analysis of the Secondary Objective

First Secondary Objective: Negative predictive value, positive predictive value, sensitivity, and specificity will be calculated. Prediction will be performed using a Cox regression model with the following predictors: platelet expression of Fc γ RIIa, sex, age, and clinical risk factors associated with increased cardiovascular risk. Evaluation of the model's error rates will be based on a leave-one-out cross-validation approach. Additional models will evaluate the performance of the predictive model using a continuous measure of Fc γ RIIa with the performance of predictive models using various binary measures of Fc γ RIIa.

Second Secondary Objective: The adjusted Cox proportional hazards model described for the primary objective analysis will be used to compare the bleeding risk as a function of Fc γ RIIa expression. One

model will include FcγRIIa as a continuous variable, and another using the dichotomized version of FcγRIIa selected as the optimal version for risk stratification.

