The predictive capacity of platelet expression of Fc $\gamma$ RIIa was evaluated. The sensitivity of high expression to identify patients with cardiovascular events was 0.82 (95% CI 0.57 - 0.92) and the specificity was 0.51 (95% CI 0.43 - 0.58). MI, stroke, and death were uncommon (8% of all patients) in patients who had had an MI. The negative predictive value of low platelet expression of Fc $\gamma$ RIIa was 0.97 (95% CI 0.89 - 0.98) and the positive predictive value of high platelet expression of Fc $\gamma$ RIIa was 0.14 (95% CI 0.10 - 0.46). While identification of patients at high risk has great value, the identification of patients at low risk is important to reassure clinicians that they can safely withhold therapy that is associated with a risk of complications. As is often the case for low prevalence events, the negative predictive value of platelet Fc $\gamma$ RIIa expression (97% [95% CI 89% - 98%]) offers potentially important guidance to clinicians.

A key objective of this study is to determine the optimal threshold of platelet Fc $\gamma$ RIIa expression that classifies patients as high and low risk that will, in turn, be incorporated into an individualized score designed to predict patient risk. Assessment of platelet Fc $\gamma$ RIIa expression as a continuous variable is expected to be more predictive than as a dichotomous variable. If assessment of platelet Fc $\gamma$ RIIa expression as a dichotomous variable is nearly as predictive as a continuous variable, then the simplicity associated with the definition of a threshold for high and low risk could be preferred.

Clinical criteria that identify patients at increased risk of thrombosis also identify an increased risk of bleeding (Lindholm 2019). A key feature predisposing to both thrombosis and bleeding is older age. Not surprisingly, patients identified as having an increased risk of ischemic events also exhibit a higher risk of bleeding events (Hsieh 2017, Lindholm 2019). In this pilot study, increased platelet expression of Fc $\gamma$ RIIa was not associated with a greater risk of bleeding

([name] 2018). Further, a meta-analysis of platelet function tests demonstrated that patients with high platelet reactivity were at lower risk of bleeding events compared with those who exhibit low platelet reactivity (Aradi 2015).

In summary, preliminary results demonstrate:

- Increased platelet FcγRIIa expression is associated with consistently increased platelet reactivity

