### **Current Study**

Confirmation of results seen in the single center pilot study is necessary in a larger multicenter trial to validate the results of the pilot study and to determine whether platelet expression of FcγRIIa can be used to guide individualized precision therapy and improve outcomes. Results from the current study will determine the prognostic implications of platelet FcγRIIa expression as well as the optimal manner in which to use platelet FcγRIIa expression. The analysis plan will include assessment of platelet FcγRIIa expression as a continuous variable as well as a sensitivity analysis designed to determine whether FcγRIIa  $\geq 11,000/\text{platelet}$  is the optimal threshold for discrimination of risk. In addition, it will provide key preliminary evidence regarding prognostic implications of platelet FcγRIIa expression associated with anti-thrombotic regimens and support plans for a subsequent clinical trial designed to use platelet FcγRIIa expression as a precision tool.

To identify subjects at greater risk of events, subjects will be enrolled who have an increased risk of cardiovascular events based on results from the SWEDEHEART registry that analyzed 100,879 patients (Lindholm 2019). Hospitalized MI subjects with  $\geq 2$  of the following risk factors; age  $\geq 65$ , prior MI, diabetes mellitus, multivessel coronary artery disease (two or more vessels or left main with a stenosis  $\geq 50\%$  at coronary angiography) and chronic kidney disease (an estimated glomerular filtration rate below  $60 \text{ ml/min}/1.73 \text{ m}^2$ ) will be enrolled in the current study. In the SWEDEHEART registry, patients with  $\geq 2$  risk factors comprised 47% of patients and their risk of death, MI and stroke was 9.7/100 patient years. In the pilot study, 55% of subjects with increased risk based on clinical risk scores exhibited platelet expression of FcγRIIa  $\geq 11,000$  ([name] 2020). In the current study, enrollment of subjects receiving treatment with anticoagulant therapy (i.e., for treatment of atrial fibrillation, venous thromboembolism) will be limited to approximately 100 subjects. Subjects with non-cardiovascular conditions expected to limit survival to less than 2 years will be excluded in the current study.

Because high platelet expression of FcγRIIa increases platelet reactivity (Boylan 2008, Lova 2002), it is anticipated that despite an association between high platelet expression of FcγRIIa

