A final set of exploratory analyses will be done to help determine the optimal threshold value of FcγRIIa for risk stratification. Define a threshold value, x, and define “low” FcγRIIa as a value less than or equal to x, and “high” FcγRIIa as a value greater than x. Next, calculate exposure-adjusted subject incidence rates for the primary endpoint, separately for the “low” and “high” subgroups, as the number of subjects with an event divided by the sum across subjects of the event/censoring times. Then, plot the exposure-adjusted incidence rates as a function of x for each subgroup, as well as the difference between subgroups. In addition, ROC curves will be produced showing the sensitivity and specificity of FcγRIIa to predict the presence or absence of a primary endpoint, as a function of the FcγRIIa threshold.

Flow cytometry considerations

[figure not shown]
Flow cytometry output, mean fluorescence intensity (MFI), can be influenced by multiple factors. External standards are used to translate MFI into molecules/platelet. In the original study, Bangs Laboratories Quantum MESF beads were used to translate MFI to antibody binding capacity ([name] et al). Because our antibody is labeled with 1 molecule of phycoerythrin (PE) per antibody, the antibody binding capacity equates to molecules per platelet.

Shortly before initiating the current study, Bangs Laboratory changed their calculation template. The company reported that over time their calculation template had experienced a shift (personal communication). This change led to a substantial change in the quantification. The change represents a ‘unit’ change rather than a complete revision of the translation of MFI into molecules/platelet.

Results using Bangs Laboratories Quantum MESF were compared with an independent external standard, BD Quantibrite. The two external standards (Quantum MESF and Quantibrite) yielded similar results. Based on this information, the revision of the formula by Bangs Laboratories was determined to be a more accurate assessment of molecules/platelet.

Results from the original study were analyzed with the use of the Quantibrite formula to relate results obtained using the previous Bangs Laboratories formula with the formula used with Quantibrite beads.

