5.10 Determination of Sample Size

This study is designed to provide a sufficient number of events to build and evaluate a prediction model. The planned sample size of 800 subjects will continue until at least 80 ischemic events have occurred. Under the guideline from Steyerberg of 10 events required per predictor (Steyerberg 2019), this sample size will allow a model with FcγRIIa and up to seven additional predictors to be built. Preliminary results ([name] 2018) suggest that a 4-fold greater incidence of events will be seen in subjects with high platelet expression of FcγRIIa. For the primary endpoint, there will be at least 95% power to detect a 2-fold greater incidence of cardiovascular endpoints (MI, stroke, and death) with a two-sided $\alpha < 0.01$ assuming 8% of subjects experience the endpoint. With the planned sample size of 800 a hazard ratio (HR) of 1.9 with a $p=0.04$ (lower bound of the 95% CI of 1.2) can be detected. For the secondary endpoint, there will be 95% power to detect a hazard ratio of 1.93 when comparing bleeding risk in subjects with high compared with low FcγRIIa expression when assuming a two-sided $\alpha = 0.05$ and 5% of subjects experience bleeding in the low FcγRIIa expression group.

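### The search for an FcγRIIa cut-off is not placed inside the cross-validation, so data-searched cut-offs will look better than they are, also relative to the continuous measure

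*SAP*

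**What the plan says.** SAP 5.7.1 describes the search: "A final set of exploratory analyses will be done to help determine the optimal threshold value of FcγRIIa for risk stratification". The tools are plots of incidence rates below and above a moving threshold, and ROC curves. No data are held out, no resampling is mentioned, and no rule says how the plots lead to a chosen value. The same section separately fixes a cut-off of 1,750 by translating the pilot study's 11,000 to the new calibration.

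SAP 5.7.2 (and Protocol 9.4.3) sets out the prediction model and says "Evaluation of the model's error rates will be based on a leave-one-out cross-validation approach". Further models then set the continuous measure against several binary ones. The cut-offs are not listed, and nothing says which steps are repeated in each fold. The bleeding analysis later uses the "dichotomized version of FcγRIIa selected as the optimal version for risk stratification", which confirms that one version is to be picked.

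The Protocol (section 2.3, Prior study to evaluate FcγRIIa) calls finding the best threshold a key objective. It expects the continuous form to predict better, but adds that if a dichotomous form is "nearly as predictive as a continuous variable, then the simplicity associated with the definition of a threshold" could tip the choice.

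**The concern.** Leave-one-out refits the coefficients without the held-out subject. It does not undo a choice that this subject helped to make. If the cut-off was chosen on all 800 subjects, each of them is scored on a cut-off fitted partly to his or her own outcome. In the simplest case, classification by one fixed cut-off, nothing is refitted at all, so leave-one-out returns the apparent sensitivity and specificity unchanged. In the multivariable Cox model the other coefficients do move, but the choice of cut-off is still untested.

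The comparison is also uneven: the binary side enters with the best of many tries, the continuous side with one. The Protocol leans towards a threshold when the two are close, so even a modest artificial narrowing of the gap could lead the study to recommend a cut-off that the data do not support. The reported error rates would then not carry over to new patients.

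**Working it through.** **The plan's own figures.** The documents give no figure for cross-validated performance. The two nearby figures reproduce:
- Translated threshold: exp(0.9160084 × ln 11,000 − 1.0611595) = exp(8.524054 − 1.0611595) = exp(7.462895) = 1742.18 (SAP: 1742.183, rounded to 1,750).
- Model size: 80 events at "10 events required per predictor" gives 80/10 = 8 predictors (SAP: FcγRIIa plus seven).

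**Inputs from the documents.** 800 subjects and 80 events ("The planned sample size of 800 subjects will continue until at least 80 ischemic events have occurred", SAP 5.10). A high-versus-low effect of about 2 ("at least 95% power to detect a 2-fold greater incidence of cardiovascular endpoints (MI, stroke, and death", SAP 5.10). About half of subjects high ("55% of subjects with increased risk based on clinical risk scores exhibited platelet expression of" at least 11,000, Protocol 2.3, Current Study).

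**Assumptions not in the documents.** Standard normal marker; cut-off chosen by maximum Youden index J between the 10th and 90th percentiles; follow-up ended at the 80th event; a pre-specified cut-off with about 54% of subjects high. Three truths: no effect; a linear effect with high/low hazard ratio about 2; a step with hazard ratio 2.

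**Check 1: marker alone, 1,000 simulated studies per truth.** Mean J (standard errors at most 0.004):

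| Truth | Search on all, then leave-one-out | Search repeated in each fold | New data | Optimism (first − last) |
|---|---|---|---|---|
| No effect | 0.070 | 0.004 | 0.000 | 0.070 |
| Linear | 0.227 | 0.169 | 0.168 | 0.059 |
| Step | 0.196 | 0.150 | 0.151 | 0.045 |

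A cut-off fixed in advance gave J = 0.001 with no effect, so it shows no optimism.

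A separate simulation with 17 candidate cut-offs gave 0.056 against 0.000 (no effect) and 0.198 against 0.156 (linear), an excess of 0.056 and 0.042. Nesting the search returned 0.000 and 0.152.

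For the linear truth, the AUC of the continuous marker was 0.626. The searched cut-off appeared to reach 0.613, a gap of 0.013. In new data it reached 0.584, a gap of 0.042. With nesting the gap was 0.626 − 0.585 = 0.041.

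**Check 2: marker plus six binary clinical predictors, 300 simulated studies per truth.** A logistic model stood in for the Cox model (common censoring time), with a one-step leave-one-out predictor and assumed prevalences and effects. Entries are AUC, binary minus continuous, and in brackets the share of studies in which binary came out ahead:

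| Truth | Search on all, then leave-one-out | Search repeated in each fold | New data |
|---|---|---|---|
| No effect | 0.579 − 0.571 = +0.008 (73%) | 0.570 − 0.571 = −0.001 (53%) | 0.583 − 0.586 = −0.003 (25%) |
| Linear | 0.636 − 0.633 = +0.003 (57%) | 0.617 − 0.633 = −0.016 (29%) | 0.629 − 0.646 = −0.017 (0.7%) |
| Step | 0.624 − 0.600 = +0.024 (95%) | 0.609 − 0.600 = +0.009 (73%) | 0.621 − 0.612 = +0.009 (85%) |

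The tilt towards binary (first column minus last) is 0.011, 0.020 and 0.015. Pooled leave-one-out AUC ran somewhat low for the models overall, so the differences are safer to read than the levels. Nesting recovers the true difference closely in all three cases, including the one where a step really exists, so it is not prejudiced against cut-offs.

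**The case against.** A reader might infer that the SAP prescribes leave-one-out after the cut-off has been fixed. It does not: the order of the steps is not stated, and what can be shown is an omission. The omission does not rescue the plan, though. If leave-one-out covers the binary models without a repeated search, the choice is unvalidated. If it covers only the main model, the searched cut-offs get apparent performance. Only a nested search avoids the problem, and a reading of plots without a rule cannot be rerun about 800 times. Showing every threshold without picking one would also be harmless, but SAP 5.7.2 says that one is picked.

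Other stronger readings fail too:
- That all reported error rates are biased. The continuous model and 1,750 involve no search in this study.
- That the comparison is decided in favour of a cut-off. No document says that the best-scoring version wins. With the marker alone and a linear effect, the searched cut-off still lost to the continuous marker in 83% of simulated studies; with clinical predictors it won in 57%. The result depends on metric and model.
- That the bleeding analysis is biased in the same way. Its cut-off is chosen on a different outcome and no cross-validation is planned there.
- That leave-one-out must be abandoned. Nested leave-one-out works.

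It also stands that SAP 5.7.1 calls the search exploratory and that the primary test uses the continuous marker. But 5.7.2 carries the product of the search into the secondary objectives without that label.

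**Conclusion.** The point holds for data-searched cut-offs only. As written, the plan never validates the choice of cut-off. At 80 events this overstates the Youden index of a searched cut-off by about 0.04 to 0.07 and shifts the binary-versus-continuous AUC difference by about 0.01 to 0.02 towards binary. In the marker-only linear case it shrinks a true AUC gap of 0.042 to an apparent 0.013, which matters when the Protocol's test is whether the two forms are close. These sizes rest on a normal marker, a Youden search or a grid of cut-offs, and assumed covariate effects; the direction does not depend on those choices. The primary analysis is untouched. The sponsor should correct this before the threshold analyses are run.

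**What to change.** In SAP 5.7.2:
- State a rule for selecting the cut-off: the criterion and the range of values searched.
- Rerun the whole procedure, including that search, in every resample. Nested leave-one-out, repeated 10-fold cross-validation and bootstrap optimism correction would all serve.
- Report corrected sensitivity, specificity, PPV and NPV for searched cut-offs.
- Report the corrected continuous-minus-binary difference in performance with a 95% CI, and rest any statement that a cut-off is close enough on that interval. A simple ranking is too noisy: even with nesting, binary came out ahead in 29% of linear-effect studies when it was truly better in 0.7%.
- Report the fixed 1,750 cut-off separately as the pre-specified binary comparison; it needs no correction for search.

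The cost is SAP wording and computing time, with no new data. The reported performance of searched cut-offs will look slightly worse.

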#### 9.4.2 ANALYSIS OF THE PRIMARY OBJECTIVE

Cox proportional hazards models will be fit to compare the risk of the primary endpoint based on platelet expression of FcγRIIa as a continuous variable. Subjects will be followed until their earliest MI, stroke, or death. Patients who do not experience the composite endpoint will be censored at their last telephone follow-up. Time to the primary endpoint will be calculated as days from study enrollment. Models will be adjusted for potential confounders including sex and other subject demographics and medical history collected at baseline. In the pilot study, it was observed that older age, diabetes mellitus, and prior revascularization were associated with higher platelet FcγRIIa expression.

A set of sensitivity analyses will evaluate FcγRIIa as a binary endpoint, which each analysis using a different threshold for classifying FcγRIIa as high or low. In particular, these analyses will explore whether a binary or a continuous measure of FcγRIIa provides greater predictive value, and whether or not a threshold of  $\geq 11,000/\text{platelet}$  is optimal.

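### The FcγRIIa prediction models are given only yes/no classification measures, with no risk cut-off, prediction time or calibration check, and no measure is named for comparing the continuous and binary forms of the marker

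*SAP*

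**What the plan says.** SAP 5.7.2, first secondary objective, opens with the measures: "Negative predictive value, positive predictive value, sensitivity, and specificity will be calculated". Protocol 9.4.3 has the same sentence. Prediction uses a Cox model with FcγRIIa, sex, age and clinical risk factors; the protocol lists these factors as MVD, CKD, DM and prior MI. On validation the SAP says: "Evaluation of the model's error rates will be based on a leave-one-out cross-validation approach". The comparison of marker forms follows in the same paragraph: "Additional models will evaluate the performance of the predictive model using a continuous measure of" FcγRIIa, set against models with various binary versions. What counts as performance there is not defined.

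Protocol 9.4.2 raises the same question among its sensitivity analyses: "these analyses will explore whether a binary or a continuous measure of FcγRIIa provides greater predictive value". It names no measure either. Protocol 2.3 (prior study) makes the threshold a key objective and expects the continuous form to predict better. It adds that if the binary form does nearly as well, "the simplicity associated with the definition of a threshold for high and low risk could be preferred". How close is close enough is not stated.

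The nearest full-range analysis is in SAP 5.7.1: "ROC curves will be produced showing the sensitivity and specificity of FcγRIIa to predict the presence or absence of a primary endpoint". It is exploratory, varies the threshold of the marker alone, and names no area under the curve.

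**The concern.** A Cox model gives each subject a continuous predicted risk, and the outcome is a time to event. All four named measures, and an error rate, need that risk cut at some value and the outcome fixed at some time. The plan gives neither. With 12 months of accrual and at least 18 months of follow-up after the last enrolment, subjects are observed for about 18 to 30 months. An event status with no fixed time therefore treats unequal observation as equal.

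Measures taken at one cut change only when a subject crosses it. Two models that rank subjects differently on either side of the cut can look alike. That matters because the protocol would accept the simpler binary marker if it performs nearly as well, and a blunt measure makes the two forms harder to tell apart.

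Separately, the score is meant to determine the risk of MI, stroke and death. Sensitivity and specificity at a percentile cut do not change if every predicted risk is doubled. At an absolute cut they may move, but they do not show how far the predicted risks are off. Nothing planned checks whether predicted risks agree with observed ones.

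**Working it through.** **Figures from the documents.**
- Sample size: "The planned sample size of 800 subjects will continue until at least 80 ischemic events have occurred" (SAP 5.10). At 10 events per predictor, 80/10 = 8, which is FcγRIIa plus seven. This reproduces.
- Threshold: exp(0.9160084 × ln 11,000 − 1.0611595) = 1,742.18, rounded to 1,750 (SAP 5.7.1). This reproduces.
- Expected events: 10% per year (Protocol 4.1) over a mean of 2 years gives 800 × (1 − exp(−0.2)) = 800 × 0.181 = 145. So 80 is the minimum and about 145 the expectation.
- Effect: 2-fold planned, 4-fold in the pilot (SAP 5.10).
- Share with high FcγRIIa: 55% (Protocol 2.3).

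**Assumptions not in the documents.** Log-normal marker with SD of the log 0.4; sizes of the clinical effects; and the cut on predicted risk. The cuts tried were the median, top 25%, top 20%, the event rate, and the cut with the best sensitivity plus specificity.

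**Method.** Trials of 800 subjects were simulated with 18-30 months of follow-up. Cox models used FcγRIIa plus sex, age, MVD, CKD, DM and prior MI. The true marker effect was either continuous (log-linear) or a step at 1,750. Continuous and binary models were compared on leave-one-out linear predictors, with 1,500-2,000 trials per cell. The Monte Carlo standard error is about 1 point, for example √(0.3 × 0.7 / 1,500) = 0.012. For each criterion:

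mismatch rate = P(the non-generating form scores better) + ½ P(tie)

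| High/low HR | Events | Generating form | C-index | Sensitivity + specificity, over cuts |
|---|---|---|---|---|
| 2 | 80 | continuous | 12% | 26-33% |
| 2 | 80 | step at 1,750 | 17% | 29-37% |
| 2 | 145 | continuous | 7% | 20-27% |
| 2 | 145 | step | 8% | 21-29% |
| 4 | 80 | continuous | 0.7% | 4-25% |
| 4 | 80 | step | 1.3% | 5-21% |
| 1.5 | 80 | continuous | 25% | 37-42% |
| 1.5 | 80 | step | 36% | 41-46% |

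Cross-validated partial likelihood at HR 2 and 80 events gives 10% (continuous) and 13% (step).

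**Ratios from the rounded table.** At HR 2 and 80 events: 26/12 = 2.2 to 33/12 = 2.8 (continuous), and 29/17 = 1.7 to 37/17 = 2.2 (step). At HR 1.5: 37/25 = 1.5 to 42/25 = 1.7, and 41/36 = 1.1 to 46/36 = 1.3.

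**Hand check.** At HR 2, 145 events and a continuous truth, the mean difference between the two models divided by its SD is 1.46 for the C-index and 0.59 for the median cut. A normal approximation gives Φ(−1.46) = 7.2% and Φ(−0.59) = 27.8%, against simulated 6.7% and 27.0%. Relative efficiency is (0.59/1.46)² = 0.16. Over the HR 2 settings and cuts it runs from 0.16 to 0.49.

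**Raw error rate, HR 2, 80 events.** Cut at the event rate, the mismatch is 10% if the truth is continuous but 64% if it is a step, so this measure leans to the continuous form whatever the truth. Cut at 50% risk, the figures are 53% and 42%, close to a coin toss.

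**What a mismatch costs.** A further simulation (HR 2, about 80 events, log-SD 0.30 and 0.45, 150 trials per cell, 10-fold cross-validation) scored the chosen model on a large independent sample. With a linear truth, mean C was 0.674-0.680 when chosen by C-index and 0.671-0.678 when chosen by sensitivity plus specificity. With a step truth it was 0.647 against 0.645-0.647. The average loss was about 0.001-0.004, and one mismatched choice cost about 0.01-0.03. As a rough cross-check, the extra mismatches at HR 2 and 80 events are 12-21 points, and 0.12 × 0.01 to 0.21 × 0.03 = 0.001 to 0.006.

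**The case against.** The strongest reply is that the plan sets no decision rule. A reader might infer that the four classification measures will settle which form of FcγRIIa is adopted. The documents do not say so: SAP 5.7.2 speaks of performance without defining it, and Protocol 9.4.2 only explores the question. This stands. The supportable point is that no other measure is named, and that the named ones would be inefficient if used.

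Nor is every mismatch in the table a mistake. Protocol 2.3 allows a slightly less predictive binary marker to be preferred for simplicity, while the simulation counts any numerical win. This also stands, and is why a margin is needed.

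The average cost in discrimination is small, and the gap depends on an unstated cut-off and an assumed marker distribution. Both are true. One classification measure, the error rate cut at the event rate, even matches the C-index when the truth is continuous, but it fails when the truth is a step.

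Finally, classification measures have a clinical purpose here, since Protocol 2.3 values NPV for identifying low-risk patients. That is a reason to keep them as results, but not to rely on them alone. The ROC curves in SAP 5.7.1 do not fill the gap, because they concern the marker alone and not the multivariable models.

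**Conclusion.** The point holds as a SHOULD-level improvement to a secondary analysis. SAP 5.7.2 and Protocol 9.4.3 name only classification measures for the prediction models, give no cut-off or prediction time, name nothing further for the continuous-versus-binary comparison, and plan no calibration check.

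At the planned 2-fold effect and minimum event count, using sensitivity plus specificity for that comparison would raise the mismatch rate from about 12-17% to about 26-37%. The direction is the same whichever form is true. The size depends on the marker distribution, covariate effects and cut-off assumed, and it shrinks at HR 1.5.

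A reader might go further and conclude that the final score would be badly degraded. The calculations do not support that: the average loss is about 0.001-0.004 C-index units. The primary Cox test is not affected.

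**What to change.** In SAP 5.7.2:
- Compare the continuous and binary models on their leave-one-out linear predictors, using cross-validated partial log-likelihood or the Harrell or Uno C-index.
- Report the difference with a bootstrap 95% CI and judge it against a margin, stated in advance, for when the binary form counts as nearly as predictive. The documents give no value. The sponsor should set it on the scale of the chosen measure, knowing that a mismatched choice cost only about 0.01-0.03 C-index units in simulation.
- Add a calibration slope for the chosen score.
- Keep NPV, PPV, sensitivity and specificity as descriptive results, at a stated risk cut-off and a stated prediction time, with a method that accounts for censoring.

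The cost is SAP wording and a few lines of R on predictions the leave-one-out step already produces. No new data, subjects or visits are needed. The downside is one or two extra measures to report, and a C-index difference is less familiar to clinicians than the predictive values, which are kept.
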